8.4.3 Analysis of Secondary Endpoints

The comparison between the proportions of recoveries at 12 and 24 weeks in patients treated with D-aspartate and patients treated with placebo will be analysed as the main analysis of the primary endpoint.

To evaluate for differences after treatment, between groups in other secondary endpoints, repeated measures analysis of variance (ANOVA) will be used in case of parametric continuous variables, and Mann-Whitney and Kruskal Wallis tests will be used in case of non-parametric continuous variables. For repeated measures, ANOVA sphericity will be tested by using Mauchly's test and results corrected in case of need, by using Greenhouse-Geisser method. Significance level will be set at $p<0.05$.

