Demographic and clinical characteristics at baseline will be summarized as frequency distributions (for categorical variables) and descriptive statistics of mean, standard deviation, median, minimum and maximum (for continuous variables).

The efficacy analysis will be performed in the ITT population. In order to assess the robustness of the results, the analysis of the primary endpoint will be repeated in the PP population.

The comparison between the proportions of recoveries at 8 weeks in patients treated with D-asp and patients treated with placebo will be based on descriptive statistics (difference, relative risk and/or odds ratio) and on the chi-square test.

A set of exploratory analyses is planned. First, a multiple logistic regression model will be fitted to the data with recovery at 8 weeks as the dependent variable and age, sex, current disease modifying therapy (DMT) use, disease course, severity of relapse, and random assignment as covariates, to adjust for imbalances between the treatment groups.

Second, the time to recovery will be computed for each patient and included as the dependent variable in a multivariate Cox model, with all the above mentioned variables as covariates. Patients not recovered will be censored at last observation.

All continuous or semiquantitative variables will be tested for normality and homogeneity of variance by using Kolmogorov Smirnov and Levene tests. To evaluate for differences after treatment, between groups, repeated measures analysis of variance (ANOVA) will be used in case of parametric variables, and Mann-Whitney and Kruskal Wallis test will be used in case of non-parametric variables. For repeated measures, ANOVA sphericity will be tested by using Mauchly's test and results will be corrected in case of need, by using Greenhouse-Geisser method. Significance level will be set at $p<0.05$.

Analyses of safety variables will be performed on the safety population. Safety data will be summarized descriptively.

Table 1 Schedule of Assessments

	Screening	Baseline	On treatment visits		End of treatment	Early termination
Assessments	Day -5/-3	Day 0, Week 0	Week 8 (± 3 days)	Week 12 (± 3 days)	Week 24 (± 3 days)	
VISIT	VISIT -1	VISIT 0	VISIT 1	VISIT 2	VISIT 3	VISIT ET ^A
Written informed consent ^B	X					
Demographic data	X					
Medical History/Present Conditions	X					
History of MS/MS treatment	X					
Previous and concomitant medications	X ^C	X	X	X	X	X
Physical Examination ^D	X	X	X	X	X	X

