D-asp at the dose of 2660mg or placebo will be administered once a day for 24 weeks in the form of identical oral solution preparations. The IP (D-asp or placebo) should be administered preferably after the meal.

The content of a sachet should be cleared out in an empty glass. Then approximately 100 ml of still water should be added and the product should be mixed until the effervescence is ended. The product should be administered immediately after the preparation.

Placebo will be undistinguishable from D-asp in terms of packaging, size, colour, weight, appearance, taste and mode of administration.

6.3

Assignment to Treatment Groups

Patients presenting with a relapse and meeting the eligibility criteria during a screening period of 3-5 days will be randomised in a 1:1 ratio via e-CRF to:

- D-asp,
- Placebo.

It is planned to randomise 80 patients with relapse. Randomisation will be stratified according to age (<30 years vs. \geq 30 years) and site location (Rome+Naples+Pozzilli vs. the other sites).

Patients without a relapse will be recruited only at the Pozzilli site and will be randomised in a 1:1 ratio via e-CRF to:

- D-asp,
- Placebo.

It is planned to randomise 40 patients without a relapse. Randomisation will be stratified according to age (<30 years vs. \geq 30 years)

The randomisation list will be in a balanced block design and will be centralized. In each site, eligible patients will be sequentially assigned to the next study number as they present themselves for the study, starting from the lowest number provided for each centre. If a patient discontinues from the study, the patient number will not be reused, and the patient will not be allowed to re-enter the study.

It will be the responsibility of the Investigator (or designee) to explain, and make sure patients fully understand any appropriate treatment related information.

6.4

Non-investigational Medicinal Products to be Used

Treatment with the IP (D-asp 2660mg once daily or placebo) will be administered as add-on to conventional therapies (IFN beta-1a 44mcg TIW for patients without relapse and IFN beta-1a 44mcg TIW plus methylprednisolone i.v. for patients with relapse, for 5 consecutive days at 1000mg once daily).

The prescription of IFN beta-1a in the individual patients will be totally independent from his/her inclusion in the study.

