- A urine pregnancy test will be performed in female patients to exclude pre-existing pregnancy (is not required if the patient is postmenopausal or surgically sterilized or if a serum pregnancy test was already performed within 7 days before the Baseline visit);
- Administration of the EDSS;
- Administration of the 25-FWT, the 9HPT, the Symbol Digit Modalities Test and the Low Contrast Letter visual Acuity Test;
- Administration of the MFIS and of the Fatigue Severity Scale;
- Patients satisfying all eligibility criteria will be randomised to the assigned treatment group;
- IP will be dispensed to patients with directions for use. Patients will be reminded to return the unused IP at the next visit;
- Neurophysiological assessments (LTP and recruitment curve) will be performed in patients without relapse enrolled at the centre of the PPD [REDACTED]
- A blood sample will be collected (before receiving corticosteroids) for immune-phenotype and immunometabolic analysis in patients enrolled in the centres of Rome, Naples and Pozzilli;
- A brain MRI will be performed whenever possible, according to local clinical practice;
- Adverse events occurred from the previous visit and/or during this visit will be recorded;

Once all procedures and assessments for this visit are completed, an appointment for the next visit will be made.

Visit 1 (Week 8)

The following procedures and assessments will be performed at this Visit:

- Any change in concomitant medications will be recorded;
- Physical examination including height, weight, BMI, waist circumference, blood pressure, heart rate;
- Neurological examination;
- A blood sample will be collected for haematology and blood chemistry tests, according to local clinical practice;
- A urine sample will be collected for routine urinalysis, according to local clinical practice;
- Administration of the EDSS;
- Administration of the 25-FWT, the 9HPT, the Symbol Digit Modalities Test and the Low Contrast Letter visual Acuity Test;
- Administration of the MFIS and of the Fatigue Severity Scale;
- Neurophysiological assessments (LTP and recruitment curve) will be performed in patients without relapse enrolled at the centre of the PPD
- A blood sample will be collected for immune-phenotype and immunometabolic analysis in patients enrolled in the centres of Rome, Naples and Pozzilli;
- IP will be returned by patients and compliance to therapy will be evaluated.

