7.7 Other Assessments

Neurophysiological assessment

Neurophysiological assessments (LTP and recruitment curve) will be performed at the centre of the PPD [REDACTED] only in the scheduled 40 patients without relapse, at baseline (Visit 0, Day 0-Week 0), and after 8 (Visit 1), 12 (Visit 2) and 24 (Visit 3) weeks from the first day of treatment with D-asp/placebo, as well as at the ET visit in case of treatment discontinuation.

MEPs will be evoked through a figure-of-eight coil connected to a Magstim 2002 magnetic stimulator and recorded from the right first dorsal interosseus (FDI) muscle with surface cup electrodes. Coil position will be adjusted to find the optimal scalp site to evoke motor responses in the contralateral FDI. The intermittent theta-burst stimulation (iTBS) protocol will consist of 10 bursts, each burst composed of three stimuli at 50 Hz, repeated at a theta frequency of 5 Hz every 10 seconds for a total of 600 stimuli (200 s duration) will be delivered over the motor "hot spot" of the FDI through a Magstim Rapid2 stimulator. The effect of iTBS on corticospinal excitability will be quantified by measuring the amplitude of MEPs evoked by a constant intensity TMS pulse delivered over the motor "hot spot". Twentyfive MEPs will be collected before iTBS (baseline) and at two different time points (0 and 15 min) after the end of the stimulation procedure. Post iTBS MEP amplitudes will then be averaged and normalized to the mean baseline amplitude. A recruitment curve, resting and active motor thresholds and paired pulse measurements of intracortical inhibition and facilitation will also be recorded at each TMS experimental session to evaluate cortical functional integrity, and trans-synaptic transmission. MEP amplitudes elicited by single TMS pulses of increasing intensity (110, 130 and 150% of the RMT) will be measured to calculate recruitment curves of the motor cortex.

8 Statistics

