8.2.2 Secondary Endpoints

The secondary endpoints of the study will be:

- Proportion of patients with recovery in their MS related disability measured at 12 and 24 weeks through the FSS of the EDSS (Visual, Brainstem, Pyramidal, Cerebellar, Sensory, Bowel/Bladder and Ambulation score);
- MS-related disability and cognitive impairment measured through the 25-FWT, the 9HPT, the Symbol Digit Modalities Test and the Low Contrast Letter visual Acuity Test (Polman and Rudick, 2010; Drake et al, 2010) during a clinical relapse at 8, 12 and 24 weeks;
- Fatigue, measured through the MFIS (Fisk et al, 1994) and the Fatigue Severity Scale (Krupp et al, 1989), at baseline during a clinical relapse and 8, 12 and 24 weeks after the onset of the relapse;
- LTP through TMS at baseline and 8, 12 and 24 weeks after the beginning of treatment, in patients without relapse;
- Immune-metabolic response of the lymphocytes in treated patients *in vitro* (glycolysis, mitochondrial respiration, fatty acids oxidation and circulating adipocytokines).

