8.4 Description of Statistical Analyses

8.4.1 General Considerations

Methods described here represent the outline of the intended methods.

A Statistical Analysis Plan (SAP) will be produced before the database lock and will contain full details of all planned summaries, listings and analyses.

All summaries and listings will be performed using Statistical Analysis Software (SAS) System software (version 9.2 or later). Unless otherwise specified, all statistical hypotheses will be tested at the 5% significance level ($\alpha = 0.05$) against two-sided alternatives, and corresponding 95% confidence intervals (CI) will be reported as appropriate.

For endpoints measured over time, descriptive statistics (for continuous variables) or frequency count (for categorical data) will be summarized by each time point.

Demographic and clinical characteristics at baseline will be summarized as frequency distributions (for categorical variables) and descriptive statistics of mean, standard deviation, median, minimum and maximum (for continuous variables).

All collected variables will be tested for normality and homogeneity of variance by using Kolmogorov Smirnov and Levene tests.

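### The plan for the continuous secondary endpoints leaves the role of baseline and the treatment contrast undefined and adjusts for neither baseline nor the randomisation strata; a baseline-adjusted mixed model fixed in the SAP would be a cheap gain in precision.

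*Combined protocol and SAP*

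**What the plan says.** Section 8.4.3 gives one rule for every secondary endpoint other than the recovery proportions: "repeated measures analysis of variance (ANOVA) will be used in case of parametric continuous variables, and Mann-Whitney and Kruskal Wallis tests will be used" for variables classed as non-parametric. It adds Mauchly's test and the Greenhouse-Geisser correction. No covariate, stratum, visit, model term or estimate is named.

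The material for a sharper analysis is already collected:

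- **Baseline.** The Visit 0 list in section 7.1 includes "Administration of the MFIS and of the Fatigue Severity Scale" and the functional tests. Sections 7.6 and 7.7 put baseline immune samples and TMS at the same visit. Section 8.2.2 lists baseline beside the follow-up weeks: "LTP through TMS at baseline and 8, 12 and 24 weeks after the beginning of treatment", and for fatigue "at baseline during a clinical relapse and 8, 12 and 24 weeks after the onset of the relapse".
- **Strata.** Section 6.3 states: "Randomisation will be stratified according to age" (under 30 against 30 or over) in both cohorts, and also by site group in the relapse cohort.

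Covariates appear only in the exploratory models of the primary endpoint (8.4.2). Section 8.4.1 presents the methods as an outline: "A Statistical Analysis Plan (SAP) will be produced before the database lock and will contain full details of all planned summaries, listings and analyses".

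**The concern.** The rule covers the 25-foot walk, 9-hole peg test, Symbol Digit Modalities Test, low-contrast acuity, both fatigue scales, LTP and the immune measures. The same sentence can be read as at least four analyses:

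- a group effect on post-baseline visits;
- a group main effect with baseline as one of four time levels;
- a group-by-time interaction;
- a change-from-baseline contrast.

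These differ widely in power. Post-baseline values alone do poorly when visits are strongly correlated, and change scores do poorly when they are weakly correlated. A model that uses baseline as a covariate avoids both losses. If no contrast is fixed before unblinding, the choice also stays open until results can be seen. Precision matters most for LTP, with only 20 patients per arm.

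**Working it through.** **Inputs from the documents.** Relapse cohort 80 patients, so 40 per arm; non-relapse cohort 40, so 20 per arm (6.3). Immune measures in 80 patients, so 40 per arm, with post-baseline samples at Weeks 8 and 12 only (5.1, 7.6). Two-sided 5% by default (8.4.1). The plan's only sample-size figure is for the primary endpoint. Its 40 per arm (40% against 70%, one-sided 5%, 80% power) is reproduced by the continuity-corrected formula. No such figure exists for the endpoints discussed here.

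**Assumed, because the documents give nothing.** SD 1; constant effect of 0.5 SD at every post-baseline visit; equal correlation rho between all visits; no dropout; contrast is the mean of the k post-baseline visits (k = 3, or 2 for immune measures).

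**Formulas.** Per-patient variance of each contrast:

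- post-baseline only: v = (1 + (k−1)rho)/k
- baseline-adjusted: v − rho²
- change from baseline (1 df): v + 1 − 2rho

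Power is from the noncentral t with noncentrality 0.5/√(2·variance/n) and 2n−2 degrees of freedom (2n−3 if adjusted).

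Example, rho 0.5, k = 3, n = 40: v = 2/3; adjusted variance 0.667 − 0.25 = 0.417; change variance 0.667 + 1 − 1 = 0.667. Noncentrality is 3.46 adjusted and 2.74 for the other two, giving 92.8% and 77.2%.

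| Power (%) at rho | 0.1 | 0.3 | 0.5 | 0.7 |
|---|---|---|---|---|
| 40 per arm, adjusted | 94.2 | 91.2 | 92.8 | 97.8 |
| 40 per arm, post-baseline only | 93.7 | 85.6 | 77.2 | 69.5 |
| 40 per arm, change | 52.2 | 62.8 | 77.2 | 93.7 |
| 20 per arm (LTP), adjusted | 69.3 | 63.8 | 66.5 | 79.0 |
| 20 per arm, post-baseline only | 68.3 | 56.0 | 47.1 | 40.6 |
| 20 per arm, change | 29.1 | 35.8 | 47.1 | 68.3 |
| Immune, adjusted | 85.2 | 83.9 | 87.8 | 95.7 |
| Immune, post-baseline only | 84.6 | 78.2 | 72.2 | 66.8 |
| Immune, change | 47.6 | 57.7 | 72.2 | 90.9 |

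At 40 per arm with three visits, the gain over the better of the two unadjusted readings is 0.5, 5.6, 15.6 and 4.1 points.

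**Effect of the unnamed contrast.** In simulation (4,000 runs, 40 per arm), the four-visit group main effect, the group-by-time test and the post-baseline group effect had power 54%, 61% and 77% at rho 0.5, and 46%, 85% and 69% at rho 0.7. Type I error across all methods and settings was 4.6% to 5.6%.

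**Weak baseline.** Keep rho 0.5 between post-baseline visits but let baseline correlate only 0.1, 0.2 or 0.3 with them. The adjusted variance is 0.667 − 0.01, − 0.04 or − 0.09. Power is 77.8, 79.7 and 82.8% against 77.2% at 40 per arm, and 47.6, 49.4 and 52.7% against 47.1% at 20 per arm. For immune measures it is 72.8, 74.6 and 77.6% against 72.2%.

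**Strata.** If they explain 5% of the residual variance (assumed; rho 0.5), adjusted power rises from 92.8% to 93.9% at 40 per arm and from 66.5% to 68.7% at 20 per arm.

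**Fading effect.** With effects of 0.5, 0.25 and 0 SD at Weeks 8, 12 and 24 (mean 0.25; rho 0.5; 40 per arm; adjusted), the averaged contrast has 40% power against 72% for Week 8 alone.

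**The case against.** - **The ANOVA may use baseline.** This stands. A reader might infer that the plan ignores the baseline value. Section 8.2.2 lists baseline among the time points for fatigue and LTP, so baseline may be a level of the time factor, and a group-by-time test would then use it. Only rank tests on raw visit values would leave it out. What the text supports is that the role of baseline is unstated and that there is no adjustment for it.
- **The SAP will settle it.** Partly. Section 8.4.1 promises full detail before database lock, and section 6.10 keeps the blind until the primary analysis is complete, so the route is open. No separate SAP text is among the documents, so nobody can say that these points stayed undefined. But a SAP that only elaborates 8.4.3 would keep the ANOVA and rank tests and would not add adjustment.
- **Nothing here is wrong.** Correct. The simulated type I error is close to 5%, and section 8.1 calls the study exploratory.
- **The gain may be small.** This stands for much of the list. Relapse-cohort baselines are taken during a relapse, and LTP is already scaled within session: "Post iTBS MEP amplitudes will then be averaged and normalized to the mean baseline amplitude". Either could leave baseline a weak predictor.
- **Normality tests choose the method.** A reader might infer this from the synopsis, where "All continuous or semiquantitative variables will be tested for normality and homogeneity of variance by using Kolmogorov Smirnov and Levene tests" stands just before the choice of method. The order suggests it, but no sentence says it, so the point does not rest on it.

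**Conclusion.** The point holds as a worthwhile, low-cost improvement in precision and clarity. In every case computed, baseline adjustment does at least as well as the better of the post-baseline-only and change readings. At 40 per arm with three visits the gain over the better one runs from under 1 point (rho 0.1) to about 16 points (rho 0.5), and is about 1 to 6 points if baseline correlates only 0.1 to 0.3 with later visits. Adjusting for strata adds about 1 to 2 points under the assumption shown. All of this rests on assumed correlations, a constant 0.5 SD effect and complete data. It is not evidence that the ANOVA is invalid, and it does not touch the primary endpoint or its sample size. The unnamed contrast is the firmest part, because it follows from the text alone.

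**What to change.** In the SAP, before unblinding, replace the ANOVA for two-arm comparisons with one mixed model for repeated measures on post-baseline values:

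- **Terms:** the Visit 0 pre-treatment value, treatment, visit, treatment-by-visit, and the cohort's own strata. These are age and site group with relapse; age without relapse; and age plus cohort for the pooled immune measures, where site group is constant. Visit 0 must be named because the functional and fatigue tests are also done at Screening.
- **Estimation:** a small-sample degrees-of-freedom correction, and a stated simpler covariance structure as fallback at 20 per arm.
- **Contrast:** one per endpoint, named in advance: either a single visit or the average over the scheduled post-baseline visits. The SAP should note that the average loses power if the effect fades.

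Kruskal-Wallis can stay where more than two groups are compared, for example with the healthy controls in section 7.6.

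**Cost:** SAP wording and a standard SAS procedure, with no new visits or data. There are two downsides. The model assumes data are missing at random, which withdrawal triggered by relapse or steroid use (5.5.1, 6.5.2) may violate. It also gains little where baseline barely predicts outcome. Worst-rank scoring of uncompleted timed tests, pre-set transformations and a missing-not-at-random analysis are optional additions and not part of this point.

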8.4.4 Analysis of Safety and Other Endpoints

Treatment emergent adverse events (TEAEs) will be those that started on or after the IP intake. All TEAEs will be summarised by Medical Dictionary for Regulatory Activities (MedDRA) System Organ Class (SOC) and Preferred Term (PT). In tables showing the overall incidence of AEs, patients who experienced the same event on more than one occasion are counted only once in the calculation of the event frequency.

Descriptive summaries of laboratory data and vital signs will be provided for actual values and changes from baseline at each visit. Shift tables with reference to range of normal values will also be used in the analysis of laboratory data.

The results of physical examination and ECG will be analysis by descriptive statistics.

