5.3.2 Exclusion Criteria

All patients (with or without relapse) will be excluded from this study if they meet any of the following criteria:

- Patients with diagnosis of primary progressive MS (PP-MS);
- Patients have any disease other than MS that could better explain his/her signs and symptoms;
- Patients with any comorbidity with diseases that might alter synaptic plasticity (e.g. Parkinson Disease, Alzheimer Disease, Stroke);
- Patients receiving concomitant treatment with drugs that may alter synaptic plasticity (e.g. cannabinoids);
- Patients with history or presence of any unstable medical condition (e.g. tumor or infection, e.g. chronic infection or severe life threatening infection within the last 6 months);
- Patients who have received any corticosteroids therapy within 3 months prior to the screening;
- Patients with any concomitant disease that may require chronic treatment with systemic corticosteroids or immunosuppressive agents during the course of the study;
- Patients who have received any immunosuppressive agents other to corticosteroids, as monotherapy or combination therapy within 3 months prior to the screening visit;
- Patients with history or currently active primary or secondary immunodeficiency;
- Patients with inadequate liver function, defined by alanine aminotransferase (ALT) $> 3 \times$ upper limit of normal (ULN), or alkaline phosphatase (AP) $> 2 \times$ ULN, or total bilirubin $> 2 \times$ ULN if associated with any elevation of ALT or AP;
- Patients with inadequate bone marrow reserve, defined as a white blood cell count less than $0.5 \times$ lower limit of normal (LLN);
- Patients with moderate to severe renal impairment;
- Patients unable to complete an MRI (contraindications for MRI include but are not restricted to weight ≥ 140 kg, pacemaker, cochlear implants, presence of foreign substances in the eye,

intracranial vascular clips, surgery within 6 weeks of entry into the study, coronary stent implanted within 8 weeks prior to the time of the intended MRI, etc). Patients with contraindication to Gd can be enrolled into the study but cannot receive Gd contrast dyes during their MRI scans;

- Patients with contraindication to gadolinium (Gd) can be enrolled into the study but cannot receive Gd contrast dyes during their MRI scans;
- Patients receiving supplements that, in the Investigator's opinion, may affect the evaluation of fatigue;

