Abnormal laboratory findings and other abnormal investigational findings (for example, on an ECG trace) should not be reported as AEs unless they are associated with clinical signs and symptoms, lead to treatment discontinuation or are considered otherwise medically important by the Investigator. If a laboratory abnormality fulfils these criteria, the identified medical condition (for example, anaemia, increased ALT) must be reported as the AE rather than the abnormal value itself.

Serious Adverse Events

An SAE is any untoward medical occurrence that at any dose:

- Results in death.
- Is life-threatening. (Note: The term “life-threatening” refers to an event in which the subject is at risk of death at the time of the event, not an event that hypothetically might have caused death if it was more severe.)
- Requires inpatient hospitalization or prolongs an existing hospitalization.
- Results in persistent or significant disability or incapacity.
- Is a congenital anomaly or birth defect.
- Is otherwise considered to be medically important. (Note: Important medical events that may not result in death, be life-threatening, or require hospitalization may be considered as SAEs when, based upon appropriate medical judgment, they may jeopardize the subject or may require medical or surgical intervention to prevent one of the outcomes listed above. Examples of such events include allergic bronchospasm requiring intensive treatment in an emergency room or at home, blood dyscrasias or convulsions that do not result in inpatient hospitalization, or the development of drug dependency or drug abuse.)

For the purposes of reporting, any drug interactions, medication errors, overdose, abuse, misuse, off-label use, occupational exposure, lack of efficacy reports or suspected transmission of an infectious agent via an IP is also considered an SAE, as described in Section 7.4.1.4.

Events that Do Not Meet the Definition of an SAE

Elective hospitalizations to administer, or to simplify study treatment or study procedures (for example, an overnight stay to facilitate chemotherapy and related hydration therapy application) are not considered SAEs. However, all events leading to unplanned hospitalizations or unplanned prolongation of an elective hospitalization (for example, undesirable effects of any administered treatment) must be documented and reported as SAEs.

Events Not to Be Considered as AEs/SAEs

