8.2.3 Other Endpoints

The following safety parameters will be evaluated:

- Incidence, severity, and relationship to treatment of treatment-emergent adverse events (TEAEs);
- Incidence, severity, and relationship to treatment of SAEs;
- Clinically significant changes in routine haematology, chemistry and urinalysis laboratory tests;

C
C
I

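### The normal-range laboratory shift tables cannot show worsening within the abnormal category, although patients may enter with ALT up to 3 × ULN, AP up to 2 × ULN or WBC down to 0.5 × LLN

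*Combined protocol and SAP*

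**What the plan says.** Section 8.4.4 plans two laboratory outputs. The first is continuous: "Descriptive summaries of laboratory data and vital signs will be provided for actual values and changes from baseline at each visit". The second is categorical: "Shift tables with reference to range of normal values will also be used in the analysis of laboratory data". The text states no bands in multiples of the normal limit, no toxicity grading of laboratory values and no table of the worst on-treatment value.

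Section 8.2.3 lists as a safety endpoint "Clinically significant changes in routine haematology, chemistry and urinalysis laboratory tests". It gives no numeric criterion, and 8.4.4 does not say how such changes will be counted.

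The liver criterion in Section 5.3.2 excludes a patient only if ALT exceeds 3 × ULN, if AP exceeds 2 × ULN, or if total bilirubin exceeds 2 × ULN together with some elevation of ALT or AP. The marrow criterion excludes "Patients with inadequate bone marrow reserve, defined as a white blood cell count less than" 0.5 × LLN.

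Section 7.4.1.1 says that abnormal laboratory findings "should not be reported as AEs unless they are associated with clinical signs and symptoms". It adds two other routes into the AE record: the finding leads to discontinuation, or the investigator considers it medically important. Section 7.4.3 has samples analysed in each site's local laboratory and the sponsor supplied with the local normal ranges. Section 8.4.1 calls the methods an outline and defers full detail to a SAP due before database lock.

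**The concern.** A shift table against the normal range has three states for each analyte: low, normal and high. A patient who starts high can stay high or move down; a patient who starts low can stay low or move up. Neither has a cell for getting worse in the direction already abnormal. The entry limits allow such patients in for ALT, AP and WBC, and for bilirubin when it is raised alone.

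These patients start closest to the protocol's own laboratory limits, and they receive 24 weeks of D-asp or placebo on top of IFN beta-1a. If the shift table is read as the categorical safety result, a large further rise in ALT or fall in WBC appears as no movement. Any imbalance between arms then has to be found in the change-from-baseline summaries or in the AE tables.

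**Working it through.** The plan states no figure on this point, so there is nothing to reproduce. The check classifies assumed baseline and worst values under the planned table, and then asks what the other planned outputs would show.

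**Inputs**
- Entry limits: ALT at most 3 × ULN, WBC at least 0.5 × LLN (Section 5.3.2).
- Planned table: low, normal or high against the normal range (Section 8.4.4).
- Arm size: 120 patients randomised 1:1 (Synopsis), so 120/2 = 60 per arm. This assumes every patient has laboratory data. Table 1 makes these tests dependent on local practice, so the real denominator may be smaller.
- The patient values are assumptions, chosen so that each baseline meets the entry limits.

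**Step 1: classification and dilution.** ALT is high if above 1 × ULN; WBC is low if below 1 × LLN. Change = worst − baseline. Shift in the arm mean from one such patient = change/60.

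| Analyte | Baseline → worst | Planned table | Change | Shift in mean of 60 |
|---|---|---|---|---|
| ALT (× ULN) | 0.8 → 2.5 | Normal → High | +1.7 | 1.7/60 = 0.028 |
| ALT | 1.2 → 2.9 | High → High | +1.7 | 0.028 |
| ALT | 2.9 → 8.0 | High → High | +5.1 | 5.1/60 = 0.085 |
| ALT | 2.9 → 12 | High → High | +9.1 | 9.1/60 = 0.152 |
| WBC (× LLN) | 0.95 → 0.55 | Low → Low | −0.40 | −0.40/60 = −0.007 |
| WBC | 0.55 → 0.30 | Low → Low | −0.25 | −0.25/60 = −0.004 |

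The same ALT rise of 1.7 × ULN is a shift if it starts at 0.8 and no shift if it starts at 1.2. All five cases that start outside the range show no movement in the planned table.

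**Step 2: the change-from-baseline summary.** It includes all five cases, but as a mean it spreads each one over the arm. A maximum or minimum would reveal them. Section 8.4.1 names minimum and maximum only for baseline characteristics, so their use for laboratory data is not confirmed.

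**Step 3: the same cases in bands.** With ALT bands ≤1, >1–3, >3–5 and >5 × ULN, both 2.9 → 8.0 and 2.9 → 12 move from >1–3 to >5. With WBC bands ≥1, 0.5–<1 and <0.5 × LLN, 0.55 → 0.30 moves to the lowest band. ALT 1.2 → 2.9 and WBC 0.95 → 0.55 stay within one band. Three of the five hidden cases become visible, and those three are the ones that cross an entry limit. The bands narrow the gap and do not close it.

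**Step 4: number of patients.** The documents do not give the share entering above ULN or below LLN. Under an assumed 10% to 30% for a given test, the count would be 0.10 × 60 = 6 to 0.30 × 60 = 18 per arm. Nothing in the documents supports that range, so it is not a finding.

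**The case against.** A reader might infer that worsening in these patients is not shown at all, or that the plan cannot show the 8.2.3 endpoint. The documents do not support that. The sentence just before the shift tables in 8.4.4 plans actual values and changes from baseline at each visit, and a patient whose ALT rises from 2.9 to 12 × ULN contributes +9.1 × ULN there. Section 7.4.1.1 sends medically important abnormalities to the AE record and gives raised ALT as an example, and 8.4.4 tabulates treatment-emergent events. Nor does 8.4.4 say that the shift table is how the endpoint will be judged. What remains is that a group mean dilutes individual outliers and that the AE route rests on each investigator's judgement.

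A reader might also infer that early stoppers are lost. Table 1 schedules laboratory tests at the ET visit, so their samples are planned. The text does not say how they enter the by-visit summaries, which is a matter of presentation.

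Third, 8.4.1 describes an outline and promises a SAP with full summaries and listings. No such separate SAP is in the text available, and 8.2.3 breaks off at a redaction. Banded tables or listings may therefore be planned elsewhere. This stands as a limit on the point: the gap lies in what 8.4.4 states, and total omission is not proven.

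**Conclusion.** The point holds in a limited form. By construction, the only categorical laboratory analysis stated cannot show worsening within the abnormal category, and Section 5.3.2 admits patients in that position for ALT, AP and WBC. The other planned outputs cover these patients only in part: the mean change includes them but dilutes them (at most 0.15 × ULN in the ALT examples, assuming 60 patients with data per arm), and AE capture depends on judgement. Separately, the 8.2.3 endpoint has no stated criterion.

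The number of patients affected cannot be computed from the documents. It would also go too far to conclude that a D-asp signal would be missed; the documents support only that the shift tables alone would not reveal it in patients who start outside the range. This is a minor safety-reporting improvement, and the primary analysis is unaffected.

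**What to change.** In 8.4.4 or the SAP, keep the normal-range shift tables for all analytes. Replacing them would remove the planned table for every test without bands, such as haemoglobin, platelets, creatinine and electrolytes.

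Add, by arm, shift tables of the last pre-dose value against the worst post-dose value, including ET and unscheduled samples, in multiples of the local limit:
- ALT and AST: ≤1, >1–3, >3–5, >5 × ULN
- AP and bilirubin: ≤1, >1–2, >2 × ULN
- WBC: ≥1, 0.5–<1, <0.5 × LLN

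State that the cut-points at 3 × ULN for ALT, 2 × ULN for AP and bilirubin, and 0.5 × LLN for WBC come from the entry criteria. State also that the AST cut-points and the 5 × ULN cut-point are added for analysis, since Section 5.3.2 has neither. These are bands for tabulation and carry no rule for patient management.

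Do not count every band move as clinically significant: that would count ALT 0.99 → 1.01 × ULN and ignore 1.1 → 2.9 × ULN. Tabulate all moves, and prespecify before unblinding which ones count towards the 8.2.3 endpoint.

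The cost is SAP wording and a few extra descriptive tables. The laboratory values and local ranges are already to be collected (Section 7.4.3), so patients carry no added burden.
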